| AlloSCT | allogeneic stem cell transplant |
| ANC | absolute neutrophil count |
| ASCT | autologous stem cell transplant |
| AST | aspartate aminotransferase |
| AUC _{0-∞} | area under the concentration-time curve from time zero to infinity |
| AUC _{0-last} | area under the concentration-time curve from time zero to the last quantifiable concentration |
| AUC _{0-τ} | area under the concentration-time curve from time zero to the end of the dosing interval |
| β-HCG | beta-human chorionic gonadotropin |
| BMI | body mass index |
| BOR | best overall response |
| C | cycle |
| CAR | chimeric antigen receptor |
| CD | cluster of differentiation |
| C1D1 | Cycle 1 Day 1 |
| CFR | Code of Federal Regulations |
| CI | confidence interval |
| CL | clearance |
| C _{max} | maximum concentration |
| CNS | central nervous system |
| CR | complete response |
| CRO | contract research organization |
| CRR | complete response rate |
| CSR | clinical study report |
| CT | computed tomography |
| CTCAE | Common Terminology Criteria for Adverse Events |
| D | day |
| DESC | Dose Escalation Steering Committee |
| DLBCL | diffuse large B-cell lymphoma |
| DLT | dose-limiting toxicity |
| DNA | deoxyribonucleic acid |
| DOR | duration of response |
| ECG | electrocardiogram |
| ECOG | Eastern Cooperative Oncology Group |

| Abbreviation | Definition |
|---------------------|--|
| eCRF | electronic case report form |
| EDC | electronic data capture |
| EOT | end of treatment |
| EU | European Union |
| FDA | Food and Drug Administration |
| FFPE | formalin-fixed paraffin-embedded |
| FL | follicular lymphoma |
| GCP | Good Clinical Practice |
| GGT | gamma-glutamyltransferase |
| HBV | hepatitis B virus |
| HCV | hepatitis C virus |
| HD-ASCT | high-dose chemotherapy and autologous stem cell transplant |
| HIV | human immunodeficiency virus |
| hr | hour |
| IB | Investigator's Brochure |
| IC | immune cells |
| ICF | informed consent form |
| ICH | International Council for Harmonisation |
| IEC | Independent Ethics Committee |
| IgG | immunoglobulin G |
| ILD | interstitial lung disease |
| INR | international normalized ratio |
| IRB | Institutional Review Board |
| IV | intravenous |
| LFT | liver function test |
| mAb | monoclonal antibody |
| MedDRA | Medical Dictionary for Regulatory Activities |
| mmHg | millimeters of mercury |
| MRI | magnetic resonance imaging |
| MSD-ECL | Meso-Scale Discovery Electrochemiluminescence |
| MTD | maximum tolerated dose |
| NHL | non-Hodgkin lymphoma |
| ORR | overall response rate |
| OS | overall survival |
| PBD | pyrrolobenzodiazepine |
| PD | progressive disease |
| PET | positron emission tomography |
| PET-CT | positron emission tomography - computed tomography |
| PFS | progression-free survival |
| PK | pharmacokinetic(s) |
| PO | per os |
| pp | predicted probability |
| PR | partial response |
| PTT | partial thromboplastin time |
| QT | measure between Q wave and T wave in the electrocardiogram |

| Abbreviation | Definition |
|---------------------|---|
| QTcF | Fridericia correction of the QT measure |
| Q3W | every 3 weeks |
| Q4W | every 4 weeks |
| RBC | red blood cell |
| RFS | relapse-free survival |
| RR | respiratory rate |
| SAE | serious adverse event |
| SAP | statistical analysis plan |
| SCT | stem cell transplant |
| SD | stable disease |
| SOC | system organ class |
| SoE | Schedule of Events |
| SUSAR | Suspected Unexpected Serious Adverse Reaction |
| TEAE | treatment-emergent adverse event |
| TLS | tumor lysis syndrome |
| T _{max} | time to maximum concentration |
| μL | microliter |
| ULN | upper limit of normal |
| US | United States |
| Val | valine |
| WBC | white blood cell |
| WHO | World Health Organization |
| wk | week |
| WOCBP | women of childbearing potential |

Overall Summary and Rationale for Changes

Protocol Amendment 1

- [Section 3](#) [REDACTED]
- [Section 5.1](#) Inclusion criterion 8d was modified to remove exception to ALT, AST, and GGT criteria in patients with liver involvement to align with requirement to hold study drug for Grade ≥ 2 LFT increases
- [Section 5.2](#) Exclusion criterion 18 was modified to remove the exception regarding patients with prior anti-PD-1, anti-PD-L1, or anti-CTLA-4 therapy as patients who have received these therapies are excluded in exclusion criterion 2
- [Section 6.4.3](#) Dose Limiting Toxicity Definition was modified to clarify the non-hematologic DLT definition
- [Section 6.7.1](#) Premedication and [Section 6.7.3](#) Treatment and Prophylaxis of Infusion-related Hypersensitivity Reactions were modified to allow the use of IV dexamethasone
- [Section 9.8.1](#) Adverse Events was modified to align with the reporting period specified in in [Section 8.2.2](#) Eliciting and Reporting Adverse Events/Serious Adverse Events
- [Section 13.3](#) ([Appendix 3](#)) was modified to remove information related to management of toxicities in patients with hepatocellular carcinoma as no patients with hepatocellular carcinoma will be enrolled in the study
- [Protocol synopsis](#) was revised to align with the changes in the protocol
- Editorial corrections and clarifications were applied throughout

Protocol Synopsis

| | |
|-------------------------|---|
| Protocol Number: | ADCT-402-104 |
| Title: | A Phase 1 Open-Label Study to Evaluate the Safety and Antitumor Activity of Loncastuximab Tesirine and Durvalumab in Patients with Advanced Diffuse Large B-Cell Lymphoma, Mantle Cell Lymphoma, or Follicular Lymphoma |
| Sponsor: | ADC Therapeutics SA |
| Study Phase: | Phase 1b |
| Indication: | Diffuse large B-cell lymphoma (DLBCL), mantle cell lymphoma (MCL), follicular lymphoma (FL) |
| Rationale: | 
Non-Hodgkin lymphoma (NHL) is the 7th most common type of cancer in the U.S. and accounted for an estimated 4.3% of new cancer cases in 2017. It is most commonly a disease of older individuals with approximately 75% of new cases diagnosed in individuals 55 years of age or older (median age at diagnosis = 66 years). Response to initial treatment generally exceeds 50% and the overall 5-year survival rate in the U.S. is 70%. However, a significant proportion of patients will relapse. The poor prognosis for relapsed patients, especially those with chemotherapy-refractory disease with a short interval between remission and relapse, or those who relapse after high-dose therapy and autologous stem cell transplant (ASCT), highlights the need for new forms of treatment for NHL.
 
Loncastuximab tesirine (ADCT-402) is an antibody-drug conjugate (ADC) directed against human cluster of differentiation 19 (CD19) that is well tolerated and has shown activity in patients with relapsed or refractory B-cell NHL in a Phase 1 study. It is anticipated to become a component of combination therapies that increase the response rate and durability of treatment.
 
Checkpoint activation is an immune-evasion strategy that is operative in various tumors, both solid and hematological. There is pre-clinical evidence suggesting that the combination of an antibody-drug conjugate (ADC) and a checkpoint inhibitor (such as a PD-L1 blocker) may be more potent than either of the respective monotherapies (Müller et al., 2015). Early results from clinical trials combining ADCs and checkpoint inhibitors show potential increased effectiveness of the combination (Diefenbach et al., 2015; Diefenbach et al., 2016).
 |

The primary purpose of this study is to explore whether loncastuximab tesirine and durvalumab can be safely combined, and if so, identify the dose(s) and regimens appropriate for further study. In addition, the study will potentially generate preliminary evidence as to whether loncastuximab tesirine combined with durvalumab may increase the response rate and durability of response compared to previous results with either compound as a single agent.

Objectives:

Primary Objective

- To characterize the safety and tolerability of loncastuximab tesirine in combination with durvalumab, and to identify the recommended dose and schedule for future studies

Secondary Objectives

- To evaluate the antitumor effect of the combination of loncastuximab tesirine with durvalumab
- To characterize the pharmacokinetic (PK) profile of loncastuximab tesirine when given in combination with durvalumab
- To evaluate the immunogenicity of loncastuximab tesirine when given in combination with durvalumab

[REDACTED]

Endpoints:

Primary Endpoints

- Frequency and severity of adverse events (AEs) and serious adverse events (SAEs)
- Incidence of dose limiting toxicities (DLTs) during the 21 days after the first durvalumab dose (dose escalation only)
- Frequency of dose interruptions and dose reductions
- Changes from baseline of safety laboratory values, vital signs, Eastern Cooperative Oncology Group (ECOG) performance status, and 12-lead electrocardiograms (ECGs)

Secondary Endpoints

- Overall response rate (ORR) according to the 2014 Lugano classification as determined by the Investigator. ORR is the proportion of patients with a best overall response (BOR) of complete response (CR) or partial response (PR)
- Duration of response (DOR) defined as the time from the documentation of first tumor response to disease progression or death
- CR rate defined as the percentage of patients with a BOR of CR
- Relapse-free survival (RFS) defined as the time from the documentation of CR to disease progression or death
- Progression-free survival (PFS) defined as the time between start of treatment and the first documentation of recurrence, progression, or death
- Overall survival (OS) defined as the time between the start of treatment and death from any cause
- Concentrations and PK parameters of loncastuximab tesirine (total antibody, PBD-conjugated antibody, and unconjugated cytotoxin SG3199)
- Anti-drug antibody (ADA) titers and, if applicable, neutralizing activity to loncastuximab tesirine

[REDACTED]

[REDACTED]

[REDACTED]

[REDACTED]

[REDACTED]

Study Design:

This is a Phase 1b, open-label, single-arm combination study with a dose escalation phase (Part 1) followed by a dose expansion phase (Part 2). The study will enroll approximately 75 patients.

A standard 3+3 dose escalation design will be used. The DLT period will be the 21 days after the first durvalumab dose.

The dose expansion phase (Part 2) will consist of 3 cohorts of approximately 20 patients each, one for DLBCL, one for MCL, and one for FL, to obtain additional safety and preliminary antitumor activity information at the maximum tolerated dose (MTD)/RDE.

A Dose Escalation Steering Committee (DESC), composed of study investigators and ADC Therapeutics personnel, will be responsible for decisions concerning dose escalation.

Patient Selection:

Inclusion criteria:

1. Male or female patient aged 18 years or older
2. Pathologic diagnosis of DLBCL, MCL, or FL
3. Patients must have relapsed or refractory disease and have failed or been intolerant to standard therapy
4. Patients who have received previous CD19-directed therapy must have a biopsy that shows CD19 expression after completion of the CD19-directed therapy
5. Measurable disease as defined by the 2014 Lugano Classification
6. Patients must be willing to undergo tumor biopsy
7. ECOG performance status 0-1
8. Screening laboratory values within the following parameters:
 - a. Absolute neutrophil count (ANC) $\geq 1.0 \times 10^3/\mu\text{L}$ (off growth factors at least 72 hours)
 - b. Platelet count $\geq 75 \times 10^3/\mu\text{L}$ without transfusion in the past 7 days
 - c. Hemoglobin ≥ 9.0 g/dL (5.59 mmol/L), transfusion allowed
 - d. Alanine aminotransferase (ALT), aspartate aminotransferase (AST), and gamma glutamyl transferase (GGT) $\leq 2.5 \times$ the upper limit of normal (ULN)
 - e. Total bilirubin $\leq 1.5 \times$ ULN (patients with known Gilbert's syndrome may have a total bilirubin up to $\leq 3 \times$ ULN)
 - f. Blood creatinine $\leq 1.5 \times$ ULN or calculated creatinine clearance ≥ 60 mL/min by the Cockcroft - Gault equation

Note: A laboratory assessment may be repeated a maximum of two times during the Screening period to confirm eligibility.

9. Negative beta-human chorionic gonadotropin (β -HCG) pregnancy test within 3 days prior to start of study drug on C1D1 for women of childbearing potential
10. Women of childbearing potential must agree to use a highly effective method of contraception from the time of giving informed consent until at least 16 weeks after the last dose of study therapy. Men with female partners who are of childbearing potential must agree that they will use a highly effective method of contraception from the time of giving informed consent until at least 16 weeks after the patient receives his last dose of study therapy.

Exclusion criteria:

1. Known history of hypersensitivity to or positive serum human ADA to a CD19 antibody.
2. Previous therapy with any checkpoint inhibitor
3. Autologous stem cell transplant within 100 days prior to start of study drug (C1D1)
4. History of allogenic stem cell transplant
5. History of solid organ transplant
6. Active or prior documented autoimmune or inflammatory disorders (including inflammatory bowel disease [e.g., colitis or Crohn's disease], diverticulitis [with the exception of diverticulosis], systemic lupus erythematosus, Sarcoidosis syndrome, or Wegener syndrome [granulomatosis with polyangiitis, Graves' disease, rheumatoid arthritis, hypophysitis, uveitis, etc.]). The following are exceptions to this criterion:
 - a. Patients with vitiligo or alopecia
 - b. Patients with hypothyroidism (e.g., following Hashimoto syndrome) stable on hormone replacement
 - c. Any chronic skin condition that does not require systemic therapy
 - d. Patients without active disease in the last 5 years may be included but only after consultation with the Study Physician
 - e. Patients with celiac disease controlled by diet alone
7. Active infection including tuberculosis (clinical evaluation that includes clinical history, physical examination and radiographic findings, and tuberculosis testing in line with local practice)
8. Known seropositive and requiring anti-viral therapy for human immunodeficiency (HIV) virus, hepatitis B virus (HBV), or hepatitis C virus (HCV)
9. History of Stevens-Johnson syndrome or toxic epidermal necrolysis
10. Lymphoma with active central nervous system (CNS) involvement at the time of screening, including leptomeningeal disease
11. Clinically significant third space fluid accumulation (i.e., ascites requiring drainage or pleural effusion that is either requiring drainage or associated with shortness of breath)
12. Breastfeeding or pregnant
13. Significant medical comorbidities, including but not limited to, uncontrolled hypertension (blood pressure [BP] $\geq 160/100$ mmHg repeatedly), unstable angina, congestive heart failure

- (greater than New York Heart Association class II), electrocardiographic evidence of acute ischemia, coronary angioplasty or myocardial infarction within 6 months prior to screening, uncontrolled atrial or ventricular cardiac arrhythmia, poorly controlled diabetes, or severe chronic pulmonary disease
14. Radiotherapy, chemotherapy, or other anti-neoplastic therapy within 14 days prior to start of study drug (C1D1), except shorter if approved by the Sponsor.
 15. Major surgery within 28 days prior to start of study drug (C1D1), except shorter if approved by the Sponsor. Note: Local surgery of isolated lesions for palliative intent is acceptable.
 16. Use of any other experimental medication within 14 days prior to start of study drug (C1D1)
 17. Planned live vaccine administration after starting study drug (C1D1)
 18. Failure to recover to Grade ≤ 1 (Common Terminology Criteria for Adverse Events [CTCAE] version 4.0) from acute non-hematologic toxicity (Grade ≤ 2 neuropathy or alopecia) due to previous therapy prior to screening..
 19. Congenital long QT syndrome or a corrected QTcF interval of >470 ms at screening (unless secondary to pacemaker or bundle branch block)
 20. History of another primary malignancy except for:
 - a. Malignancy treated with curative intent and with no known active disease ≥ 5 years before the first dose of investigational product and of low potential risk for recurrence
 - b. Adequately treated non-melanoma skin cancer or lentigo maligna without evidence of disease
 - c. Adequately treated carcinoma in situ without evidence of disease
 21. History of active primary immunodeficiency
 22. Any other significant medical illness, abnormality, or condition that would, in the Investigator's judgement, make the patient inappropriate for study participation or put the patient at risk.

Estimated Duration of Patient Participation and Study Duration:

The duration of the study participation for each patient is defined as the time from the date of signed written informed consent to the completion of the follow-up period, withdrawal of consent, loss to follow-up, or death, whichever occurs first.

The study will include a Screening Period (of up to 28 days), a Treatment Period (cycles of 3, 6, and 4 weeks), and a Follow-up Period (approximately every 12 week visits for up to 2 years after treatment discontinuation).

Patients may continue treatment for up to 1 year or until disease progression, unacceptable toxicity, or other discontinuation criteria, whichever occurs first.

The end of study occurs at the last visit or last scheduled procedure for the last patient, unless the study is terminated earlier by Sponsor.

Efficacy Assessments:

- Disease assessments: Positron emission tomography-computed tomography (PET-CT)

Note: If disease is not PET avid at baseline, CT with contrast or magnetic resonance imaging (MRI) may be used for follow-up disease assessments.

The assessment method determined to identify sites of disease at baseline should be used for all subsequent assessments.

Safety Assessments:

- Physical examination
- ECOG Performance status
- Height and weight
- Vital signs
- Safety laboratories (hematology, chemistry, coagulation, urinalysis, etc.)
- Pregnancy test, if applicable
- 12 Lead-ECG (triplicate)
- AEs/SAEs, graded according to CTCAE v4.0 (or more recent)

Other Assessments:

- Blood sampling for PK, ADA

Study Drugs, Dosage, and Mode of Administration:

The dose of loncastuximab tesirine for patients treated at each dose level in Part 1 is shown below. Durvalumab will be administered every 4 weeks starting 1 week after the first dose of loncastuximab tesirine. The DLT evaluation period will be the 21 days after the first durvalumab dose.

Loncastuximab Tesirine Dose Escalation

| Dose Level | Loncastuximab tesirine | Durvalumab |
|------------|-------------------------------|----------------|
| 1 | 90 µg/kg IV on Day 1 Q3W × 2 | 1500 mg IV Q4W |
| 2 | 120 µg/kg IV on Day 1 Q3W × 2 | 1500 mg IV Q4W |
| 3 | 150 µg/kg IV on Day 1 Q3W × 2 | 1500 mg IV Q4W |

Patients who have a response of PR or SD at the 15 week assessment may receive 2 additional doses of loncastuximab tesirine given 4 weeks apart.

Patients treated in Part 2 will receive study drugs at the dose and schedule determined in Part 1.

Sample Size:

Approximately 75 patients.

**Statistical
Considerations:**

Safety analyses will be presented descriptively.

Primary antitumor activity analyses will be based on response as determined by the Investigator. ORR and CR rate with 95% CI will be presented. DOR, PFS, RFS, and OS will be analyzed using the Kaplan-Meier approach.

Schedule of Events

Table 1 Schedule of Events

| | Protocol Section | Screening | Treatment Period | | | | | | Follow-up Period (up to 2 years from EOT) Every 12 weeks | |
|------------------------------------|------------------|----------------|---|---|----|--|---|----|--|--|
| | | | Cycle 1 (3 week cycle) | | | Cycle 2 (6 week cycle) ⁹ | | | | Cycle 3 and beyond (4 week cycles) |
| Day (D) | | -28 to -1 | 1 | 8 | 15 | 1 | 8 | 15 | 1 | |
| Informed consent | 11.3 | X | | | | | | | | |
| Eligibility criteria | 5 | X | | | | | | | | |
| Demography | 9.5 | X | | | | | | | | |
| Medical/cancer history | 9.5 | X | | | | | | | | |
| Tumor biopsy | 8.5.1 | X ¹ | | | | | | | | |
| Physical examination | 8.3.1 | X | X | | | X | | | X | X |
| ECOG performance status | 8.3.2 | X | X | | | X | | | X | X |
| Height | 8.3.3 | X | | | | | | | | |
| Weight | 8.3.3 | X | X | X | X | X | X | X | X | X |
| Vital signs (BP, HR, RR, Temp) | 8.3.4 | X | X | X | X | X | X | X | X | X |
| Disease assessment ² | 8.1 | X | 6 weeks and 15 weeks after C1D1, then every 8 weeks | | | | | | X ³ | Every 12 weeks until 1 year from EOT, then every 6 months until disease progression up to 2 years from EOT |
| Hematology and Chemistry | 8.3.5 | X | X ⁴ | X | | X ⁴ | X | | X | X |
| Coagulation and Urinalysis | 8.3.5 | X | | | | | | | | |
| TSH (reflex free T3 or free T4) | 8.3.5 | X | X | | | X | | | X | X |
| Hepatitis B, C, and HIV tests | 8.3.5 | X | | | | | | | | |

| | Protocol Section | Screening | Treatment Period | | | | | | EOT | Follow-up Period (up to 2 years from EOT) Every 12 weeks |
|--|------------------|-----------|---|------------------|----|--|---|------------------|--|--|
| | | | Cycle 1 (3 week cycle) | | | Cycle 2 (6 week cycle) ⁹ | | | | |
| Day (D) | | -28 to -1 | 1 | 8 | 15 | 1 | 8 | 15 | 1 | |
| Pregnancy test, if applicable | 8.3.6 | X | X ⁴ | | | X | | | X | X |
| 12-lead ECG ⁵ | 8.3.7 Table 4 | X | X (pre-dose, EOI, and 4 hr post-dose) | X (post-dose) | X | X (pre-dose, EOI, and 4 hr post-dose) | X | X (post-dose) | X ¹¹ | X |
| Premedication | 6.7.1 | | D-1 to D2 | | | D-1 to D2 | | | D-1 to D2 for cycles containing loncastuximab tesirine | |
| Loncastuximab tesirine administration | 6.3.1 | | X | | | X | | | D8 of Cycles 5 and 6 for patients who are PR or SD at Week 15 evaluation | |
| Durvalumab administration | 6.3.2 | | | X | | | | X | X ⁸ | |
| Loncastuximab tesirine PK ⁵ sample | 8.4.1 Table 5 | | X ⁵ (pre-dose, EOI, and 4 hr post-dose) | X | X | X (pre-dose, EOI, and 4 hr post-dose) | X | X | X ⁶ (pre-dose) | X |
| Loncastuximab tesirine ADA ⁵ sample | 8.4.1 Table 5 | | X ⁵ (pre-dose) | | X | X (pre-dose) | | | X ⁶ (pre-dose) | X ⁷ |

| | Protocol Section | Screening | Treatment Period | | | | | | EOT | Follow-up Period (up to 2 years from EOT) Every 12 weeks |
|---|------------------|--|---------------------------|---|----|--|---|-----------------|-----|--|
| | | | Cycle 1 (3 week cycle) | | | Cycle 2 (6 week cycle) ⁹ | | | | |
| Day (D) | | -28 to -1 | 1 | 8 | 15 | 1 | 8 | 15 | 1 | |
| Durvalumab PK sample | 8.4.1 | | | | | | | X ¹⁰ | | |
| Concomitant medications | 6.7.6 | From ICF signature date or D-14, whichever is earlier, until 30 days after last dose of study drug(s) | | | | | | | | |
| Adverse events | 8.2 | AE/SAEs from ICF signature date within 30 days after last dose of study drug(s); thereafter, related SAEs only | | | | | | | | |
| 1 st New anti-cancer treatment | | | | | | | | | X | X |
| Survival | | | | | | | | | X | X |

Abbreviations: ADA: anti-drug antibody; AE: adverse events; BP: blood pressure; ECG: electrocardiogram; ECOG: Eastern Cooperative Oncology Group; EOI: end of infusion; EOT: end of treatment; HR: heart rate; ICF: informed consent form; PK: pharmacokinetics; RR: respiratory rate; SAE: serious AE; Temp: temperature; wks: weeks

Visit Scheduling Windows:

- Treatment Period: Visit day ± 2 days (excluding C1D1 which is the reference day).
- EOT: As soon as possible after decision to discontinue the study drug(s) but preferably within 30 days after last dose of study drug(s) unless a new anticancer treatment is planned to be administered before the 30 days, in which case EOT should be conducted before initiation of the new anticancer treatment.
- Follow-up Period: Visit day ± 14 days.

¹ Tumor biopsy should be obtained prior to study drug administration.

² Screening imaging (PET-CT) must be performed within 4 weeks prior to C1D1 and the same assessment method should be used throughout the study. Week 6 imaging should be performed prior to C3D1 and Week 15 imaging should be performed prior to C5D1. All other imaging for disease assessment for patients on study drug(s) should be performed within ± 2 weeks of the scheduled timepoint. Disease assessments should be performed at the timepoints specified even if study drug dosing is delayed. If a scan has been performed within 8 weeks of EOT, it does not need to be repeated at EOT.

³ Disease assessments to be performed in patients having discontinued study drug(s) for reasons other than disease progression.

⁴ Not needed if screening assessment was performed within 3 days prior to C1D1.

⁵ On days when loncastuximab tesirine is administered, ECG, PK, and ADA timepoints are in relation to loncastuximab tesirine dose.

⁶ Cycle 3, C5, C6, C7; see [Table 5](#).

⁷ Patients who test positive for loncastuximab tesirine ADAs may be requested to supply additional ADA samples as specified in the protocol, [Section 8.4.2](#).

⁸ Administration of durvalumab, C3D1 will be 4 weeks after C2D15.

⁹ Cycle 2 will be 6 weeks long because durvalumab administration needs to be 4 weeks apart. C3D1 will be 4 weeks after C2D15.

¹⁰ The durvalumab PK sample should be taken before durvalumab dose administration.

¹¹ Cycle 3.

1 Introduction and Background

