4.2 Screening Period

Informed consent must be obtained for each patient and documented with a signed informed consent form (ICF) prior to any study procedures. Procedures that are performed as part of standard of care may be used to satisfy screening requirements if they are performed in the screening window.

The screening period is from 28 days to 1 day prior to the start of the study drug. The screening assessments should be performed within this period in order to assess the eligibility of the patient against the inclusion and exclusion criteria ([Sections 5.1](#) and [5.2](#), respectively).

See [Section 5.3](#) for the information to be collected on screening failures.

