4.3 Treatment Period

The treatment period starts on the date when a patient receives the first dose of study drug and continues until the End of Treatment (EOT) visit.

The treatment will start with Cycle 1, which will be 3 weeks long (i.e., 21 days), Cycle 2 will be 6 weeks long because durvalumab administration needs to be 4 weeks apart, and all other subsequent cycles will be 4 weeks long. Loncastuximab tesirine will be administered as an intravenous (IV) infusion over 30 minutes on Day 1 of Cycles 1 and 2. All patients will receive loncastuximab tesirine every 3 weeks (Q3W) for 2 cycles. Patients who have a response of PR or stable disease (SD) at the Week 15 assessment may receive an additional 2 doses of loncastuximab tesirine given on day 8 of Cycles 5 and 6.

Durvalumab will be administered as an IV infusion over 60 minutes on Day 8 of Cycle 1 and Day 15 of Cycle 2, then on Day 1 of subsequent cycles.

Patients may continue treatment for up to 1 year or until disease progression, unacceptable toxicity, or other discontinuation criteria ([Section 7](#)), whichever occurs first.

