6.3.2 Durvalumab Dosing

Administration of durvalumab will be performed by the Investigator or a qualified designee.

Durvalumab will be administered at a fixed dose of 1500 mg every 4 weeks. Durvalumab will be administered on Day 8 of Cycle 1, Day 15 of Cycle 2, and Day 1 of subsequent cycles.

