6.7 Premedication and Supportive Care

6.7.1 Premedication

Unless contraindicated, administer dexamethasone 4 mg PO or IV twice daily:

- the day before each loncastuximab tesirine administration (if possible),
- the day of loncastuximab tesirine administration (first dose at least 2 hours prior to administration when not given the day before; otherwise any time prior to administration), and
- the day after loncastuximab tesirine administration.

Patients who experience an infusion-related hypersensitivity reaction will receive the alternative premedication regimen specified in [Section 6.7.3](#).

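### Table 1 times Cycle 5 and 6 premedication to Day 1, the durvalumab day, although loncastuximab tesirine is given on Day 8: a minor scheduling inconsistency with a risk of site error

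*Protocol*

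**What the plan says.** - **Table 1, Premedication row.** The entry is D-1 to D2 in Cycle 1 and again in Cycle 2. In the column for Cycle 3 and beyond it is "D-1 to D2 for cycles containing loncastuximab tesirine". The row refers the reader to Section 6.7.1.
- **Table 1, loncastuximab row, same column.** "D8 of Cycles 5 and 6 for patients who are PR or SD at Week 15 evaluation". Section 4.3 agrees: "an additional 2 doses of loncastuximab tesirine given on day 8 of Cycles 5 and 6".
- **Section 6.3.2.** Durvalumab is given on "Day 8 of Cycle 1, Day 15 of Cycle 2, and Day 1 of subsequent cycles", so Day 1 of Cycles 5 and 6 is a durvalumab day.
- **Section 6.7.1.** Dexamethasone 4 mg twice daily, unless contraindicated, on three days tied to the loncastuximab dose. The list opens with "the day before each loncastuximab tesirine administration (if possible") and continues with the dosing day and the day after it.
- **Table 1, footnote 5.** "On days when loncastuximab tesirine is administered, ECG, PK, and ADA timepoints are in relation to loncastuximab tesirine dose". Premedication is not named.
- **Sections 6.7.1 and 6.7.3.** "Patients who experience an infusion-related hypersensitivity reaction will receive the alternative premedication regimen specified in" Section 6.7.3. Three of the four items there carry a Day 1 label for every cycle, and the fourth places the loncastuximab dose on Day 1.

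**The concern.** Day 1 is the loncastuximab day in Cycles 1 and 2, so D-1 to D2 is correct there. The same days are repeated for the later cycles, although loncastuximab has moved to Day 8 and Day 1 now belongs to durvalumab.

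Sites commonly work from the schedule table. One that took this cell as cycle days, without checking Section 6.7.1 or the dosing row, would give the steroid around durvalumab and none around loncastuximab. What is at stake is steroid cover for the optional late loncastuximab doses.

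**Working it through.** **Inputs.** Cycle lengths are 21, 42 and then 28 days (Section 4.3). Loncastuximab is given on D1 of Cycles 1 and 2 and, if continued, on D8 of Cycles 5 and 6 (Section 4.3). The steroid course covers dose day -1, 0 and +1 (Section 6.7.1). The visit window is ±2 days (Table 1 notes). D-1 is taken as the day before D1, which agrees with Section 4.2: "The screening period is from 28 days to 1 day prior to the start of the study drug".

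**Calendar.** With C1D1 as study day 1:

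- C2D1 = 1 + 21 = 22
- C3D1 = 22 + 42 = 64
- C4D1 = 64 + 28 = 92
- C5D1 = 92 + 28 = 120, so C5D8 = 127
- C6D1 = 120 + 28 = 148, so C6D8 = 155

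As a check, durvalumab then falls on days 8, 36, 64, 92, 120 and 148, each 28 days apart, as the protocol intends.

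**Comparison, with the Table 1 entry read as cycle days.** Day 0 denotes the day before C1D1.

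| Cycle | Loncastuximab day | Table 1 course | Section 6.7.1 course | Days shared |
|---|---|---|---|---|
| 1 | 1 | 0, 1, 2 | 0, 1, 2 | 3 of 3 |
| 2 | 22 | 21, 22, 23 | 21, 22, 23 | 3 of 3 |
| 5 | 127 | 119, 120, 121 | 126, 127, 128 | 0 of 3 |
| 6 | 155 | 147, 148, 149 | 154, 155, 156 | 0 of 3 |

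The Table 1 entry is reproduced for Cycles 1 and 2 but not for Cycles 5 and 6. The gap from the last steroid day to the loncastuximab dose is 127 - 121 = 6 days in Cycle 5 and 155 - 149 = 6 days in Cycle 6.

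**Visit windows do not close the gap.** In Cycle 5 the latest D1 is day 122, so that course ends on day 123. The earliest D8 dose is day 125, so the required course starts on day 124. There is still no shared day, and the gap is 125 - 123 = 2 days. At the other extreme, D1 on day 118 gives a course ending on day 119 and the latest dose is day 129, a gap of 10 days. Cycle 6 is the same, 28 days later.

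**Dose.** A full course is 4 mg × 2 × 3 days = 24 mg. The day before is required only where possible, so a compliant course may be 4 mg × 2 × 2 days = 16 mg. Hence 24 mg is an upper limit.

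**Exposure.** A patient who takes both optional doses receives 2 + 2 = 4 loncastuximab doses, of which at most 2 are affected.

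**The case against.** The strongest reply is that the protocol already gives the right answer. The row cites Section 6.7.1, which is unambiguous. The Day 8 dosing stands in the next row of the same column, and a site cannot schedule the dose from Table 1 without seeing it. The cell's restriction to loncastuximab cycles shows which drug the steroid serves, and D-1 to D2 could be shorthand for the day before to the day after that dose.

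Much of this stands. It makes an actual error unlikely, and it rules out a stronger reading: a reader might infer that the protocol tells sites to leave late loncastuximab doses uncovered. It does not, because Section 6.7.1 covers each dose.

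It does not remove the inconsistency. The column's day header is 1, the adjacent cell uses D8 as a cycle day, and the same notation is a correct cycle-day statement in Cycles 1 and 2. Footnote 5 shows that the protocol anchors timing to the loncastuximab dose when it means to, and it does so only for ECG, PK and ADA. The cell gives the right days only if its own notation is reinterpreted.

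A reader might also infer that Section 6.7.3 contradicts Section 6.7.1 or cannot be followed. Neither is supported. It replaces 6.7.1 for patients with an earlier infusion reaction, it times the pre-infusion drugs to the start of the loncastuximab infusion, and it allows institutional standard of care. Its Day 1 labels are out of step with Day 8 dosing, which makes it ambiguous and no more.

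**Conclusion.** The inconsistency is real in the current text, and it is minor. Read as cycle days, the Table 1 course in Cycles 5 and 6 is centred on durvalumab, ends a nominal 6 days before loncastuximab, and shares no day with the Section 6.7.1 course. The result rests on the nominal cycle lengths and on reading D-1 to D2 as cycle days, which is the natural reading but not the only one.

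The consequence is a risk of site error, confined to patients with a partial response or stable disease at Week 15 who take the optional doses. The documents do not say how many did, and they report no misplaced course.

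A reader might infer that the dose-finding results are compromised. They are not: the DLT period is the 21 days after the first durvalumab dose, nominally ending on day 8 + 21 = 29, whereas the first affected course would start on day 119. No endpoint or planned analysis depends on the premedication days. SAP Section 3.3 records that the trial ended early, so the remaining benefit within this trial may be small.

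**What to change.** 1. In Table 1, reword the premedication cell for Cycle 3 and beyond as: *day before to day after each loncastuximab tesirine dose, per 6.7.1 (nominally D7 to D9 of Cycles 5 and 6)*. Anchoring it to the dose keeps it right when a visit moves within its window or a dose is held; the cycle days are there only for orientation.
2. In Section 6.7.3, delete the Day 1 labels in all four items and keep the existing timing relative to each loncastuximab infusion. Relabelling them as the day of infusion would not work, because the dexamethasone given 12 hours before may fall on the previous evening.

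The cost is two wording edits, with no added visit, sample or procedure. A separate amendment may not be worthwhile for a terminated trial, but the edits should be carried into any later protocol that reuses this schedule. SAP Section 4.6 already provides a separate listing of premedication, so the sponsor can check at no extra cost whether any Cycle 5 or 6 dose was affected.
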